### **5.9.3. Sensitivity Analyses**

#### **5.9.3.1. Treatment Effect based on Actual Treatment Received**

Should a discrepancy between the study treatment received and the randomized treatment assignment occurred in 4 or more subjects, a sensitivity analysis may be conducted based on the study treatments that subjects actually received using the MMRM analysis method described in [Section 5.9.2](#).

#### **5.9.3.2. Impact of Missing Values Handling**

Whilst every effort will be made to prevent avoidable missing values during the study conduct ([National Research Council, 2010](#)), it is unrealistic to expect no missing values in clinical trials. The impact of missing values on the analysis results will be assessed by the sensitivity analyses described below.

### Under Missing at Random (MAR) Assumption

Multiple imputation (MI) will be performed to replace each missing value with a set of plausible values that represent the uncertainty about the correct value to impute. The Markov chain (MCMC) method will be utilized for the mITT set. SAS PROC MI will be used with MCMC method, assuming multivariate normality, to generate 25 possible imputed datasets: Each of these datasets will be analyzed using PROC MIXED in SAS using the MMRM model as described in [Section 5.9.2](#). The results of the analyses of the datasets will be combined using PROC MIANALYZE to produce an inferential result.

### Considerations of Data Potentially Missing Not at Random (MNAR)

A pattern mixture model (PMM) approach will be used to address potential MNAR patterns. The following three patterns of subjects in the mITT set will be considered:

1. Subjects with no missing values from discontinuation or from initiation of prohibited concomitant medication during treatment period (No missing)
2. Subjects with missing values from the types of ICEs below will be considered having MNAR:
  - a. Subjects who discontinue due to reasons, as recorded on the eCRF, of lack of efficacy, adverse events related to schizophrenia defined by AEHLGT of Schizophrenia and other psychotic disorders, physician decision, and withdrawal by subject
  - b. Subjects who initiated concomitant prohibited medications (ATC classifications of BUTYROPHENONE DERIVATIVES, INDOLE DERIVATIVES, and OTHER ANTIPSYCHOTICS) after the first dose of IMP and prior to the last dose of IMP with use duration of use of at least 4 days will be considered having a potential confounding ICE. The efficacy data post the start of ICE will be treated as missing with the missing pattern of MNAR.

The MNAR cases will be identified and documented prior to database lock and unblinding ([Section 9.5](#)).

3. Subjects with missing values from the type of ICEs below will be considered as having MAR
  - a. Missing values after discontinuation due to reasons, as recorded on the eCRF, of death, pregnancy, loss to follow-up, adverse event unrelated to schizophrenia, non-compliance, site termination, and COVID-19 control measures will be considered as MAR.

The missing data with MNAR pattern #2 above in the active treatment groups will be imputed tipping point analysis. A set of shift parameters to encapsulate the change in efficacy associated with MNAR due to ICEs for each of the active treatment groups will be applied in the tipping point multiple imputation analysis as described in [Ratitch et al. \(2013\)](#). It is noted, however, MNAR in the placebo group will be imputed as MAR using the standard multiple imputation method.

The MAR pattern #3 above will be imputed using the standard multiple imputation method described above.

Other missing values due to missed visits/assessments before endpoint or discontinuation will also be assumed as MAR and imputed using the standard multiple imputation method for all three patterns.

Core codes for MAR and MNAR imputations are provided in [Section 9.6](#).

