8.3.7 Adverse Events of Special Interest

All AESIs should be reported according to the procedures and timelines for SAEs (see [Section 10.3.4](#)).

The following events will be reported as AESIs:

- AEs that result in the discontinuation of IMP including those resulting from elevations in liver test results (see [Section 10.6](#))
- Heart rate >120 bpm
 - Confirm heart rate by ECG
 - Repeat heart rate measurement 30 and 60 minutes after participant is at rest
 - Report as an AESI and notify the medical monitor if heart rate remains >120 bpm 60 minutes after initial elevation OR if it is not sinus tachycardia
 - Continue to follow the participant as clinically appropriate
- QTcF is >500 ms or the QTc value represents a >60 ms increase from Baseline
 - Repeat ECG
 - Report as an AESI and notify the medical monitor
 - Repeat ECGs every 30 minutes until QTcF <450 ms or improves to <30 ms from baseline value
 - Continue to follow the participant as clinically appropriate if QTcF does not improve
- Systolic blood pressure reading (average of triplicates) ≥160 mmHg but <200 mmHg and/or diastolic blood pressure reading ≥100 mmHg but <120 mmHg
 - Repeat blood pressure measurements after 5 minutes of participant at rest in a quiet room. If blood pressure (average of triplicates) reading continues to be ≥160 mmHg systolic and/or ≥100 mmHg diastolic, additional blood pressure measurements should be performed after 30 minutes and 60 minutes from the initial elevation
 - If blood pressure elevation continues to be ≥160 mmHg systolic and/or ≥100 mmHg diastolic 60 minutes after initial elevation, report as an AESI and notify the medical monitor
 - Withhold IMP

- Consider referring participant to a health care facility for further evaluation and treatment as appropriate
- Resume IMP only upon consultation with the medical monitor
- Systolic blood pressure ≥ 200 mmHg and/or diastolic blood pressure ≥ 120 mmHg
 - Repeat blood pressure measurements after 5 minutes of participant at rest in a quiet room. If blood pressure (average of triplicates) reading continues to be ≥ 200 mmHg systolic and/or ≥ 120 mmHg diastolic, additional blood pressure measurement should be performed after 30 minutes from the initial elevation
 - If blood pressure continues to be ≥ 200 mmHg systolic and/or ≥ 120 mmHg diastolic after 30 minutes from initial elevation, report as an AESI and notify the medical monitor

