9.3.2 Primary Endpoint/Estimand Analyses

The primary estimand has the following attributes:

1. Treatments as randomized
2. mITT population as the primary population of interest
3. Change from Baseline to Week 6 in total PANSS score as the primary endpoint of interest
4. The population level summary of interest is the treatment differences estimated based on the least square mean and the corresponding 95% confidence interval from the MMRM model with treatment, visit, and treatment by visit interaction as fixed effect, participant as a random effect, and baseline PANSS score as a covariate. An unstructured covariance structure will be used for the repeated measures. The Kenward-Roger approximation will be used to estimate the denominator degrees of freedom. If the unstructured covariance matrix results in convergence issue, the heterogeneous Toeplitz covariance structure followed by the heterogeneous first-order autoregressive (AR(1)) structure will be used. If a reduced covariance matrix becomes necessary, the sandwich variance estimator will be used.
5. To address ICEs with the primary outcome data available, a treatment policy strategy will be used to include all collected outcomes in the primary statistical analysis, consistent with the intent-to-treat principle. The only exception will be the cases of concomitant use of protocol prohibited other antipsychotic and, in such cases, the data collected under the influence of confounding ICEs will be treated as missing.
6. To address ICE of trial or treatment discontinuation with no outcome data collected post discontinuation, the primary analysis of MMRM described above will be followed by PMM approach with varying level of shift parameters for missing values due to discontinuations that are potentially missing not at random (MNAR), including discontinuation due to lack of efficacy or due to adverse events. This will be implemented using delta adjustment imputation method. Further details will be described in the SAP.

The statistical hypothesis testing on the primary endpoint (H_1 and H_2 above) will be based on the estimated treatment difference from the model at Week 6. The evaluation of other time points will also be derived from the same model.

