### 9.6.2. Imputation of Missing Not at Random (MNAR) Cases

The MNAR cases will be imputed using a tipping point analysis. Subjects identified in [Section 9.5](#) who were treated with values of 'Emraclidine' will have their imputed values that occurred following an ICE shifted by delta. Delta will be defined based on a percentage (10%-90%) of the mixed effect repeated measures model least-square means difference estimate at each visit relative to each 'Emraclidine' arm from the primary endpoint analysis.

First, the SAS code in [Section 9.6.1](#) will be used to generate 25 possible imputed datasets using PROC MI. Then, the delta shift will be applied to these imputed datasets using the code below:

```
data ShiftX;
set Out1X;
if CRIT1FL = 'Y' and DCSRELFL = 'Y' and TRT ^= 'Placebo' then do;
  if AVISITN > VISITN then do;
    AVAL = AVAL0 + DELTA;
    if AVAL > MAX then AVAL = MAX
    if missing < AVAL < MIN then aval = MIN;
    if ABLFL ^= 'Y' then CHG = AVAL - BASE;
  end;
run;
```

Here, TRT is an indicator variable representing treatment with values of 'Placebo' excluded from the delta adjustment, CRIT1FL is an indicator variable representing imputed records with values

of 'Y' indicating a record was imputed, DCSRELEF is an indicator variable representing type of missingness with values of 'Y' indicating an MNAR case, AVISITN is a variable representing the analysis visit, VISITN is a variable representing the subject's last visit prior to the ICE, AVAL0 is a variable representing the original imputed value for the response variable (e.g., PANSS total score or CGI-S severity score) prior to the delta shift, DELTA is a variable representing the shift applied to each imputed value for subjects with treatment values of 'Emraclidine' that occurred after a subject's ICE, AVAL is a variable representing the new value for the response variable following the delta shift, MAX is a variable representing the maximum possible value for the response variable (e.g., 210 for PANSS total score), MIN is a variable representing the minimum possible value for the response variable (e.g., 30 for PANSS total score), ABLFL is an indicator variable flagging the visit that represents the subject's baseline value, BASE is a variable representing the baseline value for the response variable, and CHG is a variable representing the new calculated response variable based on BASE and AVAL.

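### SAP 5.9.3.2 leaves dropouts recorded as a non-schizophrenia adverse event unshifted in the MNAR analysis, although Protocol 9.3.2 names adverse-event dropout without limit

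*SAP*

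**What the plan says.** Protocol 9.3.2 item 6, repeated in the synopsis, follows the primary MMRM with a pattern mixture model using a range of shifts. It applies to discontinuations that are potentially "missing not at random (MNAR), including discontinuation due to lack of efficacy or due to adverse events". The type of adverse event is not restricted. Further details are left to the SAP.

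SAP 5.9.3.2 divides the mITT participants by recorded eCRF reason. Besides lack of efficacy, the shifted pattern 2a contains "adverse events related to schizophrenia defined by AEHLGT of Schizophrenia and other psychotic disorders, physician decision, and withdrawal by subject". Pattern 2b adds participants who took a listed class of antipsychotic for at least 4 days while on IMP. The unshifted pattern 3a contains, among other reasons, "adverse event unrelated to schizophrenia, non-compliance, site termination, and COVID-19 control measures will be considered as MAR". For that group, "The MAR pattern #3 above will be imputed using the standard multiple imputation method described above".

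The code in SAP 9.6.2 follows the same rule. The shift is conditional on "if CRIT1FL = 'Y' and DCSRELFL = 'Y' and TRT ^= 'Placebo' then do", where DCSRELFL marks an MNAR case. On its size: "Delta will be defined based on a percentage (10%-90%) of the mixed effect repeated measures model least-square means difference estimate". SAP 5.10.3 applies the same sensitivity analyses to CGI-S.

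**The concern.** The protocol names two kinds of dropout for the delta adjustment, and the SAP takes most of one of them out. SAP 5.9.3.2 gives no reason, and SAP Section 6 (Changes in the Planned Analyses) does not mention it.

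The split is also uneven. Two emraclidine participants may leave because of the same side effect. If one is recorded as an adverse event and the other as withdrawal by subject, only the second is shifted. The better-documented tolerability dropout gets the more favourable assumption.

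At stake is what a robustness claim would cover. This is the only planned analysis that departs from MAR in the unfavourable direction. A statement that the PANSS or CGI-S result withstands MNAR assumptions would silently exclude a class of dropout that the protocol said would be included.

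**Working it through.** **1. Rules side by side.** I read the pattern 3a wording as the complement of the MedDRA high-level group term used in pattern 2a.

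| Recorded reason | Protocol 9.3.2 | SAP 5.9.3.2 | Shift on emraclidine |
|---|---|---|---|
| Lack of efficacy | named, item 6 | 2a | delta |
| AE in the psychotic-disorders group term | named, item 6 (all AEs) | 2a | delta |
| Any other AE | named, item 6 (all AEs) | 3a | 0 at every delta |
| Physician decision, withdrawal by subject | not named | 2a | delta |
| Qualifying antipsychotic use | set to missing, item 5 | 2b | delta |

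The third row is the mismatch. The fourth shows that the SAP also widened the rule elsewhere.

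**2. Whether another analysis fills the gap.** The main MMRM (SAP 5.9.2) assumes MAR. The multiple imputation in SAP 5.9.3.2 also assumes MAR. The endpoint-completer analysis leaves out those without a Week 6 PANSS and is labelled MCAR. None of them gives a non-schizophrenia AE dropout a worse outcome than MAR predicts.

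**3. The plan's own figures** (Protocol 9.5, SAP 1.2). Inputs: effect size 0.48 (7/14.6 = 0.479; 8/16.7 = 0.479), two-sided alpha 0.05, power 90%.
- n per arm = 2(1.960 + 1.282)²/0.48² = 91.2, so 92; the t-test version gives 92.2, so 93. This reproduces the plan.
- Power at 93 per arm is 0.905 (t-test 0.903).
- Randomized per arm: 93/(1 − 0.25) = 124, and 3 × 124 = 372. Planned dropouts per arm: 124 − 93 = 31.

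**4. Size of the omitted shift.** Let p be the share of an active arm that drops out for a non-schizophrenia AE, f the share of the effect removed, and D the planned difference. The Week 6 difference then falls by p × f × D. D = 7 is from the plan. p is an assumption, because the documents give no rate.
- p = 3%: 0.03 × 7 = 0.21 points at f = 1; 0.19 at the 90% cap.
- p = 10%: 0.10 × 7 = 0.70 points at f = 1; 0.63 at the cap.
- In whole participants, 3, 6 and 12 of 124 give 0.17, 0.34 and 0.68 points at f = 1, and 0.15, 0.30 and 0.61 at the cap.
- Ceiling, if all 31 planned dropouts were of this type: 7 × 31/124 = 1.75 points; 1.57 at the cap.
- With the alternative D = 8, 12 of 124 gives 0.77 points; 0.70 at the cap.

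Under the SAP as written, f = 0 for these participants at every delta.

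**The case against.** **Latitude.** The protocol speaks of potentially MNAR data and leaves details to the SAP. That allows the SAP to set the shifts and define the patterns. It does not readily stretch to moving a named class into the MAR pattern without a stated reason. It does mean that an added scenario would be an adequate remedy.

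**Coverage.** A reader might infer that tolerability dropouts on emraclidine are never stress-tested. The SAP does not support that. Those recorded as physician decision or withdrawal by subject are shifted, as are those with qualifying antipsychotic use under pattern 2b. The gap is confined to a recorded non-schizophrenia AE without such use.

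**Bias.** A reader might also infer that MAR imputation overstates the drug effect. SAP 5.9.1 applies a hypothetical strategy to treatment discontinuation, so the outcome had the participant continued is the target, and assigning no benefit answers a different question. The imputation in SAP 9.6.1 also uses each participant's own baseline and observed visit scores. This objection stands against the word bias. It does not explain the split, because under the same strategy the SAP still shifts lack of efficacy, physician decision and withdrawal.

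**Frequency.** Protocol 8.3.7 lists as special interest "AEs that result in the discontinuation of IMP including those resulting from elevations in liver test results", but that is a reporting rule and gives no rate or arm imbalance. Protocol 2.2.3 found no clear dose relationship for blood pressure in participants with schizophrenia. Heart rate did appear dose dependent in Part A, without tachycardia reported as a TEAE. Protocol 2.3 speaks only of a potential for increases. The documents therefore do not show that such dropouts will be many or concentrated on active drug.

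**Significance.** One can construct a result that crosses 0.05. SE = 14.6 × √(2/93) = 2.14. A 4.5-point difference has z = 2.10 (p = 0.036); losing 10% leaves 4.05, z = 1.89 (p = 0.058). That needs an assumed rate and a chosen result. A 10% loss changes the conclusion only for differences between about 4.20 (1.96 × 2.14) and 4.66 (4.20/0.9). At the planned 7 points it leaves 6.3, z = 2.94 (p = 0.003).

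**Conclusion.** The protocol-SAP mismatch is real and unexplained. For emraclidine dropouts whose recorded reason is an AE outside the psychotic-disorders group term, and who have no qualifying antipsychotic use, the only MNAR analysis of PANSS and CGI-S applies no shift, whatever the delta.

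The likely size is modest: about 0.2-0.7 PANSS points, or 0.2-0.6 at the delta cap. That rests on an assumed 3-10% of an active arm, loss of the full planned 7 points, and every such participant missing Week 6. At lower rates it is negligible. It matters mainly for a near-threshold result, which is the situation a tipping-point analysis is meant to examine. The documents support neither a claim of bias in the primary estimate nor a forecast that significance would be lost. The individual classifications in SAP 9.5 could not be checked, but the written rule is clear.

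**What to change.** In SAP 5.9.3.2, widen pattern 2a to discontinuation for any adverse event and delete the entry for adverse events unrelated to schizophrenia from pattern 3a. The current narrower rule can stay as a second run. At the least, add the wider rule as a further tipping-point scenario beside the present one, and state why the narrower rule departs from Protocol 9.3.2. Update the blinded MNAR case list (SAP 9.5) and the DCSRELFL flag before database lock and unblinding. The change carries over to CGI-S through SAP 5.10.3.

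The cost is SAP wording and a blinded re-flag of cases; how many is unknown. The sensitivity result may become slightly less favourable.

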#### Under Missing Completely at Random (MCAR) Assumption

An additional sensitivity analysis will be conducted on the Endpoint Completer set using the MMRM analysis method described in [Section 5.9.2](#).

#### **5.9.4. Subgroup Analyses**

Subgroup analyses of the primary endpoint will be made based on the mITT set to assess consistency of the intervention effect across the following subgroups:

- Age group:  $< 40$  vs  $\geq 40$  years
- Sex: Male vs Female
- Baseline PANSS Total Score:  $\leq$  baseline median vs  $>$  baseline median (median of the mITT set regardless treatment group)
- Baseline CGI-S:  $\leq$  baseline median vs  $>$  baseline median (median of the mITT set regardless treatment group)
- Race: White vs Black
- Region: United State vs Other Countries

If the number of subjects within a subgroup is too small (less than 10% of the mITT set), the subgroup categories may be redefined prior to unblinding the study. Provided that the sample sizes in the subgroups allow, the MMRM analysis method described in [Section 5.9.2](#) will be applied to the subgroup analysis. Cohen's D will not be summarized for the subgroup analysis. The treatment effect across subgroups will be summarized by forest plots.

#### **5.10. Key Secondary Efficacy Analyses**

##### **5.10.1. Secondary Estimand**

The key research question for the first secondary efficacy variable will be addressed with an estimand based on the following attributes:

1. Treatments: treatments as randomized regardless of the actual treatment received.
2. Target study population of interest: mITT population.
3. Endpoint of interest: Change from Baseline to Week 6 in CGI-S score.
4. Population level summary of interest treatment differences estimated based on the least square mean and the corresponding 95% confidence interval from the MMRM model of the emraclidine groups and placebo group in the endpoint of interest.

5. Strategy for Intercurrent events (ICEs): A hypothetical strategy to address ICEs of potential death, treatment discontinuations, missed visits, and start of prohibited concomitant medications will be utilized. The data after the start of prohibited concomitant medications (ATC classifications of BUTYROPHENONE DERIVATIVES, INDOLE DERIVATIVES, and OTHER ANTIPSYCHOTICS) after the first dose of IMP and prior to the last dose of IMP with use duration of use of at least 4 days will be censored under the hypothetical strategy. The hypothetical strategy allows the study to assess the effect of emraclidine treatment without the confounding effect of prohibited concomitant treatments.

### **5.10.2. Main Analytical Approach**

Similar to the analysis of the primary efficacy variable, the change from baseline to each study visit in CGI-S score will be summarized by visit and treatment group. A MMRM analysis will be used with treatment, geographic region, visit, and treatment by visit interaction as fixed effect, subject as a random effect, and baseline CGI-S score as a covariate. An unstructured covariance structure will be used for the repeated measures. If the unstructured covariance matrix results in convergence issue, the heterogeneous Toeplitz covariance structure followed by the AR(1) structure will be used. The Kenward-Roger approximation will be used to estimate the denominator degrees of freedom. The difference between each emraclidine dose group and placebo at Week 6 will be estimated based on the LSMean difference between the treatment groups at Week 6 from the MMRM with the associated 95% CI and p-value. A Cohen's D value will be derived as the ratio of the estimated difference to the population standard deviation at each visit estimated from the model (the square root of the diagonal elements of the estimated covariance matrix). The missing values are assumed to be missing at random for the main analysis, including missing due to missed visits or early termination due to COVID-19 control measures. The LSM ( $\pm$ SE) from the model will be plotted for change in CGI-S score by visit and treatment group. Similarly, the mean ( $\pm$ SD) of absolute values and change from Baseline CGI-S score will be presented by visit and treatment group.

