6. To address ICE of trial or treatment discontinuation with no outcome data collected post discontinuation, the primary analysis of MMRM described above will be followed by pattern mixture model (PMM) approach with varying level of shift parameters for missing values due to discontinuations that are potentially missing not at random (MNAR), including discontinuation due to lack of efficacy or due to adverse events. This will be implemented using delta adjustment imputation method. Further details will be described in the statistical analysis plan (SAP).

The statistical hypothesis testing on the primary endpoint (emraclidine 30 mg QD vs placebo and emraclidine 15 mg QD vs placebo) will be based on the estimated treatment difference from the model at Week 6 and will be tested in a hierarchical order with each at 2-sided alpha level 0.05. The evaluation of other time points will also be derived from the same model.

The number and proportion of responders (ie, participants with 30% reduction from Baseline in the PANSS total score at Week 6 or the last assessment before discontinuation) will be summarized. A logistic regression model, with baseline PANSS as a covariate, will be used to compare the proportion of responders in each active arm with placebo. If expected counts are <5, then a Fisher's Exact test will be used.

The secondary estimand has the following attributes:

1. Treatments as randomized
2. mITT population as the primary population of interest
3. Change from Baseline to Week 6 in CGI-S score as the endpoint of interest
4. The population level summary of interest is the treatment differences estimated based on the least square mean and the corresponding 95% confidence interval from the MMRM model with treatment, visit, and treatment by visit interaction as fixed effect, participant as a random effect, and baseline CGI-S score as a covariate. An unstructured covariance structure will be used for the repeated measures. If the unstructured covariance matrix results in convergence issue, the heterogeneous Toeplitz covariance structure followed by the heterogeneous first-order autoregressive (AR(1)) structure will be used. When a reduced covariance matrix is used, the sandwich variance estimator will be used. The Kenward-Roger approximation will be used to estimate the denominator degrees of freedom.
5. ICEs will be addressed using the same strategies as described above for the primary endpoint.

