9.3.3 Secondary Endpoint/Estimand Analyses

The secondary estimand has the following attributes:

1. Treatments as randomized
2. mITT population as the population of interest
3. Change from Baseline to Week 6 in CGI-S score as the endpoint of interest
4. The population level summary of interest is the treatment differences estimated based on the least square mean and the corresponding 95% confidence interval from the MMRM model with treatment, visit, and treatment by visit interaction as fixed effect, participant as a random effect, and baseline CGI-S score as a covariate. An unstructured covariance structure will be used for the repeated measures. If the unstructured covariance matrix results in convergence issue, the heterogeneous Toeplitz covariance structure followed by the heterogeneous first-order autoregressive (AR(1)) structure will be used. When a reduced covariance matrix is used, the sandwich variance estimator will be used. The Kenward-Roger approximation will be used to estimate the denominator degrees of freedom.
5. ICEs will be addressed using the same strategies as described above for the primary endpoint

The number and proportion of participants with ≥ 1 and ≥ 2 point improvements from Baseline at the last CGI-S assessment (at Week 6 or the last assessment before discontinuation) will be summarized. A logistic regression model, with baseline CGI-S as a covariate, will be used to compare the proportion of responders in each active arm with placebo. If expected counts are < 5 , then a Fisher's Exact test will be used.

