## 1.2. Sample Size Considerations

A sample size of approximately 93 subjects in each treatment group completing the Week 6 assessments (approximately 279 in total) should provide at least 90% power to detect an effect size of 0.48 in change from Baseline in the Positive and Negative Symptom Score (PANSS) total score at Week 6 between either active treatment group versus placebo at the  $\alpha=0.05$  level. The effect size of 0.48 represents a clinically meaningful effect on symptom reduction based on large scale meta-analysis of historical data from several currently approved antipsychotic medications in common usage ([Leucht et al, 2013](#)). It could be translated into a difference of 7 points versus placebo if the standard deviation of change from baseline is 14.6 points or a difference of 8 points versus placebo if the standard deviation of change from baseline is 16.7 points. Both scenarios of the standard deviation are consistent with historical observations. To account for a discontinuation rate of approximately 25% for a 6-week treatment period (as observed in Trial CVL-231-SCH-001), it is planned to randomize approximately 372 subjects.

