### **5.9.2. Main Analytical Approach**

The change from baseline to each study visit in total PANSS score will be summarized by visit and treatment group. A MMRM analysis will be used to analyze the data from all post-randomization timepoints up to Week 6 with treatment, geographic region, visit, and treatment by visit interaction as fixed effect, subject as a random effect, and baseline PANSS score as a covariate. An unstructured covariance structure will be used for the repeated measures. If the unstructured covariance matrix results in convergence issue, the heterogeneous Toeplitz covariance structure followed by the heterogeneous first-order autoregressive (AR(1)) structure will be used. The Kenward-Roger approximation will be used to estimate the denominator degrees of freedom. The difference between each emraclidine dose group and placebo at Week 6 will be estimated based on the Least Squares Mean (LSMean) difference between the treatment groups at Week 6 from the MMRM with the associated 95% confidence interval (CI) and P-value. A Cohen's D value will be derived as the ratio of the estimated difference to the population standard deviation at each visit estimated from the model (the square root of the diagonal elements of the estimated covariance matrix). The missing values are assumed to be missing at random for the main analysis, including missing due to missed visits or early termination due to COVID-19 control measures. The LSM ( $\pm$ SE) from the model will be plotted for change in PANSS total score by visit and treatment group. Similarly, the mean ( $\pm$ SD) of absolute values and change from Baseline PANSS total score will be presented by visit and treatment group.

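### The SAP omits the protocol's sandwich variance for reduced covariance structures (5.9.2, 5.10.2), and for CGI-S names AR(1) without the word heterogeneous

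*SAP*

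**What the plan says.** Protocol 9.3.2 (PANSS total) and 9.3.3 (CGI-S), and the synopsis, start from an unstructured covariance and fall back first to heterogeneous Toeplitz, then to heterogeneous AR(1). Each attaches a variance rule. For PANSS: "If a reduced covariance matrix becomes necessary, the sandwich variance estimator will be used". For CGI-S: "When a reduced covariance matrix is used, the sandwich variance estimator will be used". Kenward-Roger degrees of freedom are named for both.

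SAP 5.9.2 (PANSS) keeps the sequence: "the heterogeneous Toeplitz covariance structure followed by the heterogeneous first-order autoregressive (AR(1)) structure will be used". It keeps Kenward-Roger and does not mention the sandwich. SAP 5.10.2 (CGI-S) says "the heterogeneous Toeplitz covariance structure followed by the AR(1) structure will be used", again with Kenward-Roger and without the sandwich. SAP Section 6 gives no account of departures from the protocol, and the revision table in Section 7 is empty.

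Three other places bear on the CGI-S wording. The SAP 5.11 table and SAP 5.12.2 send CGI-S to the MMRM of 5.9.2, which is the heterogeneous form. SAP 5.10.2 itself derives Cohen's D from a model SD for each visit.

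**The concern.** A model-based standard error is right only if the fitted covariance structure is right. A reduced structure is adopted because the full one would not fit, not because it is believed, and the protocol's sandwich rule protects the test in that case. Without it, the Week 6 standard error depends on the restriction imposed.

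The restriction matters most for plain AR(1), which forces one variance on every visit. The Week 6 standard error then reflects an average over visits. A programmer following 5.10.2 literally would fit that structure; one following 5.11 would not. If the plan stays silent, the variance estimator may be chosen after a convergence failure, when results are visible. The 5.9.2 model also serves the subgroup, exploratory and several safety analyses, so the gap carries over to them.

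**Working it through.** **1. The plan's own figures.** SAP 1.2 says the sample "should provide at least 90% power to detect an effect size of 0.48", with 93 completers per arm and two-sided alpha 0.05. Normal approximation: 0.48 × √(93/2) = 3.273; 3.273 − 1.960 = 1.313; Φ(1.313) = 0.905 (noncentral t: 0.903). The scenario "a difference of 7 points versus placebo if the standard deviation of change from baseline is 14.6 points" gives 7/14.6 = 0.479, and 8/16.7 = 0.479. Dropout: 93/0.75 = 124 per arm, 279/0.75 = 372. All reproduce. Neither document gives a figure for the fallback standard error.

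**2. What each structure restricts.** With six post-baseline visits, covariance parameters number 6 × 7/2 = 21 (unstructured), 6 + 5 = 11 (heterogeneous Toeplitz), 6 + 1 = 7 (heterogeneous AR(1)) and 2 (plain AR(1)). Only the last removes visit-specific variances.

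**3. Assumptions not in the documents.** Week 1 SD is a stated fraction of the Week 6 SD, changing linearly. Correlations are autoregressive, slowly decaying, Toeplitz or strengthening late. The 25% dropout (SAP 1.2) is taken as monotone, even over visits and completely at random. The calculation is large-sample and omits the baseline covariate.

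**4. Method.** With true covariance S and a proportion p_k last seen at visit k, fit V by minimising Σ p_k [log|V_k| + tr(V_k⁻¹S_k)]. Put A = Σ p_k V_k⁻¹ and B = Σ p_k V_k⁻¹S_kV_k⁻¹, padded with zeros to full size. The model variance is the Week 6 element of A⁻¹; the true variance is that of A⁻¹BA⁻¹. With q = √(model/true), actual alpha = 2[1 − Φ(1.96q)].

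**5. Results without the sandwich.**

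| Structure fitted | Assumed truth | q | Actual alpha |
|---|---|---|---|
| Plain AR(1) | equal SDs | 1.00–1.02 | 0.046–0.050 |
| Plain AR(1) | Week 1 SD 0.75 of Week 6 | 0.87–0.88 | 0.084–0.089 |
| Plain AR(1) | 0.6 | 0.80–0.81 | 0.115–0.119 |
| Plain AR(1) | 0.5 | 0.75–0.76 | 0.137–0.141 |
| Plain AR(1) | 0.4 | 0.71–0.72 | 0.160–0.164 |
| Plain AR(1) | 1.25 (SD falls; Toeplitz correlation) | 1.15 | 0.024 |
| Heterogeneous AR(1) | fractions 0.4 to 1.0 | 0.93–1.02 | 0.047–0.069 |
| Heterogeneous Toeplitz | fractions 0.4 to 1.0 | 0.92–1.00 | 0.050–0.070 |
| Either heterogeneous form | 40 random unstructured patterns | 0.87–0.98 | 0.054–0.087 |
| Plain AR(1) | the same 40 patterns | 0.76–1.02 | 0.045–0.135 |

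With the sandwich, q = 1.00 and alpha = 0.05 in large samples for every structure. Adding a random subject intercept to plain AR(1) left q at 0.71–0.88 when the SD rises.

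**6. Hand check of the mechanism (Week 1 fraction 0.5).** SDs are 0.5, 0.6, 0.7, 0.8, 0.9, 1.0; proportions observed are 1.00, 0.95, 0.90, 0.85, 0.80, 0.75 (sum 5.25). Pooled variance = (0.250 + 0.342 + 0.441 + 0.544 + 0.648 + 0.750)/5.25 = 2.975/5.25 = 0.567, so the pooled SD is 0.753 of the Week 6 SD. Alpha = 2[1 − Φ(1.96 × 0.753)] = 0.14, in line with the fitted 0.137–0.141.

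**The case against.** The strongest reply is that plain AR(1) is the weaker reading. SAP 5.10.2 follows 5.9.2, presents itself as similar to the primary analysis, and needs a per-visit SD for Cohen's D that plain AR(1) cannot supply; 5.11 and 5.12.2 point to 5.9.2. So the missing word is probably shorthand. This stands: the documents show an inconsistency, not a demonstrated change of model. It does not remove the need to settle which structure the program fits.

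Second, the SAP is silent on the sandwich but does not revoke it. That is fair, but the SAP restates the rest of the protocol's rule and names only Kenward-Roger, so a reader of the SAP alone would use model-based standard errors.

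Third, several conditions must coincide before the large error occurs: the unstructured fit fails, heterogeneous Toeplitz fails, 5.10.2 is taken literally, the CGI-S SD rises over visits, and both PANSS tests succeed so that H3 and H4 are reached (Protocol 9.1; SAP 5.3, 5.4). This also stands, and limits the weight of the point.

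A reader might infer that naming subject as a random effect beside an unstructured matrix makes the fallback likely. A separate random intercept would indeed be redundant. But the documents do not say that one will be coded, leaving it out cures the redundancy, and no convergence-failure rate is given.

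**Conclusion.** The point holds in a limited form. The SAP omits, without a recorded reason, a variance rule that the protocol sets for both endpoints, and its CGI-S section is inconsistent with the rest of the SAP on the last fallback structure.

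Under the assumed covariances, a heterogeneous fallback without the sandwich leaves the Week 6 standard error between 13% too small and 2% too large, with alpha about 0.05 to 0.09. That covers both PANSS fallback steps and the first CGI-S step. Plain AR(1) for CGI-S gives a standard error 12 to 29% too small and alpha about 0.08 to 0.16 if the SD rises, close to nominal if the SD is constant, and conservative (0.024) if it falls. The documents give Week 6 PANSS SDs only and no CGI-S SDs, so neither the direction nor the size can be fixed from them.

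A reader might conclude that all four hypotheses, H1 to H4, face badly wrong standard errors. The documents do not support that: both PANSS fallbacks in SAP 5.9.2 keep a variance for each visit, so the large error does not apply to H1 or H2. For H3 and H4 it needs two failed fits and the literal reading of 5.10.2.

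**What to change.** Before unblinding:

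- In SAP 5.9.2 and 5.10.2, restore the protocol's sentence that the sandwich estimator is used with any reduced covariance structure.
- In SAP 5.10.2, write heterogeneous AR(1), to agree with the protocol, 5.9.2, 5.11 and 5.12.2.
- State how degrees of freedom are obtained when the sandwich is used. Kenward-Roger adjusts the model-based variance, which the sandwich replaces; the protocol leaves this open as well.
- If the omission was deliberate, record the reason.

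The cost is a few sentences in the SAP and matching program options. No new data are needed, and nothing changes if the unstructured model converges.
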